6.6. Dose Modification

Study drug dose modification is not permitted, except for management of intolerable GI symptoms (see Section 6.7.1).

6.7. Management of Incident Diabetes

Participants who develop diabetes during the study will be

- · provided and trained to use a glucometer
- · educated on the signs and symptoms of hypoglycemia and its treatment, and
- provided a diary to record hypoglycemic episodes per Section 10.4.7.1.

Participants will be referred to their usual care provider and provided with a letter showing the study results indicative of diabetes. The decision to further evaluate, to initiate antihyperglycemic therapy, and the choice of antihyperglycemic medication will be at the discretion of the participant's usual care provider, with the exception of use of DPP-4 inhibitors and GLP-1R agonists, which are prohibited in the study. Monitoring for hypoglycemia includes capture of events as defined in Section 10.4.7.1. Date of diagnosis of diabetes will be captured in the electronic case report form (eCRF).

6.7.1. Management of Participants with Gastrointestinal Symptoms

Participants who experience intolerable GI symptoms (for example; nausea, vomiting, or diarrhea) at any time during the study, should first be counselled on dietary behaviors that may help mitigate nausea and vomiting, (for example, eating smaller meals, splitting 3 daily meals into 4 or more smaller ones, and stopping eating when they feel full). If symptoms persist, the participant should be prescribed, at the investigator's discretion, symptomatic medication (for example, antiemetic or antidiarrheal medication).

Temporary interruption

A temporary interruption of study intervention for 1 dose is permitted, provided the participant has taken the last 3 weekly doses. Study treatment should be resumed immediately, either alone or in combination with symptomatic medication, which can also be utilized to manage symptoms. Management of study intervention after interruptions >1 dose is discussed in Section 7.

Dose modification

If intolerable GI symptoms (for example, nausea, vomiting, or diarrhea) persist despite the above measures, the investigator should contact Lilly to consider reinitiating study intervention at the next lowest maintenance dose in a blinded fashion (for example, 15 mg and 12.5 mg reduced to 10 mg, 10 mg or lower reduced to placebo). Only 1 dose reduction per participant will be permitted during the course of the study. The dose modification is not allowed without prior discussion with Lilly's CRP and/or CRS.

6.8. Intervention after the End of the Study

Tirzepatide will not be made available to participants after conclusion of the study.

7. Discontinuation of Study Intervention and Participant Discontinuation/Withdrawal

7.1. Discontinuation of Study Intervention

In rare instances, it may be necessary for a participant to permanently discontinue (definitive discontinuation) study intervention. If study intervention is definitively discontinued, the participant will remain in the study to be evaluated for all planned efficacy and safety measurements. See the Schedule of Activities for data to be collected at the time of discontinuation of study intervention and follow-up and for any further evaluations that need to be completed.

Possible reasons leading to permanent discontinuation of IP:

• participant decision

o the participant requests to discontinue IP

• clinical considerations

- o initiation of GLP-1R agonist or DPP-4 inhibitor, if participants will not or cannot discontinue them
- o intolerable GI symptoms despite management as described in Section 10.8
 - *Note:* If intolerable GI symptoms persist despite symptomatic treatment, temporary drug interruption, and resumption at a lower dose of study intervention, the participant should be discontinued from the study intervention.
- o BMI ≤18.5 kg/m² with clinically significant health condition is reached at any time during the treatment period

Note: The investigator should contact the sponsor CRP and/or CRS to discuss whether it is medically appropriate for the participant to continue study treatment.

- o diagnosis of type 1 diabetes mellitus
- o diagnosis of medullary thyroid cancer after randomization
- o significant elevation of calcitonin (Section 10.4.7.3)
- o diagnosis of acute or chronic pancreatitis
- diagnosis of an active or untreated malignancy (other than basal or squamous cell skin cancer, in situ carcinomas of the cervix, or in situ prostate cancer) after randomization
- o development of any significant study intervention-related hypersensitivity reaction
- o onset of pregnancy in a female participant
- occurrence of any other treatment-emergent adverse event (TEAE), SAE, or clinically significant finding for which the investigator believes that permanent study intervention discontinuation is the appropriate measure to be taken
- o inadvertent enrollment if continued treatment with study intervention would not be medically appropriate (Section 7.2.1)
- o PHQ-9 score ≥15

- Participants should be referred to a mental health professional to assist in deciding whether the subject should be discontinued from study intervention. If a participant's psychiatric disorder can be adequately treated with psycho- and/or pharmacotherapy, then the subject, at the discretion of the investigator (in agreement with the mental health professional), may be continued in the trial on randomized therapy.
- o in addition, study intervention may be discontinued if participants:
 - answered "yes" to either Question 4 (Active Suicidal Ideation with Some Intent to Act, Without Specific Plan) on the "Suicidal Ideation" portion of the C-SSRS

or

 answered "yes" to Question 5 (Active Suicidal Ideation with Specific Plan and Intent) on the "Suicidal Ideation" portion of the C-SSRS

or

 answered "yes" to any of the suicide-related behaviors (Actual attempt, Interrupted attempt, Aborted attempt, Preparatory act or behavior) on the "Suicidal Behavior" portion of the C-SSRS.

Note: A psychiatrist or appropriately trained professional may assist in the decision to discontinue the participant.

• discontinuation due to a hepatic event or liver test abnormality

- o Participants who are discontinued from IP due to a hepatic event or liver test abnormality should have additional hepatic safety data collected via eCRF.
- Discontinuation of the IP for abnormal liver tests should be considered by the investigator when a participant meets 1 of the following conditions after consultation with the Lilly designated medical monitor:
 - ALT or aspartate aminotransferase (AST) >8× ULN
 - ALT>2× baseline value OR ≥300 U/L, whichever occurs first, if baseline ALT>2× ULN
 - ALT or AST >5× ULN for more than 2 weeks
 - ALT or AST >3× ULN and TBL >2× ULN or international normalized ratio (INR) >1.5
 - ALT or AST >3× ULN with the appearance of fatigue, nausea, vomiting, right upper-quadrant pain or tenderness, fever, rash, and/or eosinophilia (>5%)
 - ALP $>3 \times$ ULN
 - ALP >2.5× ULN and TBL >2× ULN
 - ALP >2.5× ULN with the appearance of fatigue, nausea, vomiting, right-quadrant pain or tenderness, fever, rash, and/or eosinophilia (>5%)

7.1.1. Temporary Study Drug Discontinuation

In certain situations, after randomization, the investigator may need to temporarily interrupt study drug. Every effort should be made by the investigator to maintain participants on study drug and to restart study drug after any temporary interruption, as soon as it is safe to do so. Distribution of study medication at the correct dose will be per IWRS instructions.

If study drug interruption is	then
2 consecutive doses or less	participant restarts study drug at last administered dose, as per escalation schedule.
3 consecutive doses or more	participant restarts study drug (at 5 mg, managed by IWRS) and repeats dose escalation scheme.
due to an AE	the event is to be documented and followed according to the procedures in Section 8.3 of this protocol.
due to intolerable persistent GI AE	participants should be treated as suggested in Section 10.8.

Abbreviations: AE = adverse event; GI = gastrointestinal; IWRS = interactive web response service.

Investigators should inform Lilly that study drug has been temporarily interrupted. The data related to temporary interruption of study treatment will be documented in source documents and entered on the eCRF.

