Study GPHZ is a Phase 3, multicenter, randomized, placebo-controlled, double-blinded study to evaluate the safety and efficacy of tirzepatide 10 mg and 15 mg administered subcutaneously once weekly compared with placebo when used in conjunction with a reduced-calorie diet and increased physical activity for weight management, in participants who have

- \cdot A BMI of 27 kg/m² or greater and less than 35 kg/m² and at least 2 obesity-related health problems; OR
- · A BMI of 35 kg/m² or greater and at least 1 obesity-related health problem.

Obesity-related health problems are defined as IGT, hyperlipidemia, or NAFLD.

All participants will undergo a 4-week screening period and a 72-week treatment period including a 20-week dose escalation. The safety follow-up period will be 4 weeks.

Study participants will be randomized in a 1:1:1 ratio to tirzepatide 10 mg QW, tirzepatide 15 mg QW, or placebo QW, stratified by

- baseline IGT (yes or no)
- baseline hyperlipidemia (yes or no)
- baseline NAFLD (yes or no), and
- sex (male, female).

Disclosure Statement:

This is a parallel group-treatment study with 3 arms that is participant- and investigator-blinded.

[figure not shown]
Number of Participants:

Approximately 348 participants will be screened to achieve 261 randomly assigned to study intervention for an estimated total of 87 evaluable participants per intervention group.

Intervention Groups and Duration:

All doses will be subcutaneously administered once-weekly using single-use pens. The starting dose of tirzepatide will be 2.5 mg QW (or matching placebo) for 4 weeks, then the dose will be increased by 2.5 mg (or matching placebo) every 4 weeks: 2.5 to 5 to 7.5 to 10 mg for those randomized to 10 mg, and continuing to 12.5 to 15 mg for those randomized to 15 mg.

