2.2. Background

In Japan, if obesity disease is diagnosed, the patients try lifestyle intervention including diet, exercise, and behavioral therapy for 3 to 6 months to improve body weight and health problems. If improvement of the health problems is achieved by lifestyle modification therapy, the therapy is continued. If not, and any of following criteria are met; 1) BMI \geq 25 kg/m², visceral fat area >100 cm² and 2 or more health problems, 2) BMI >35 kg/m² with 1 or more health problems. medical therapy is indicated. There remains an unmet need in the pharmacologic treatment of obesity for drugs that are safe, efficacious, and well tolerated. At present in Japan, Sanorex® (mazindol) is covered only for severely obese subjects by national health insurance with a prescription limit of 3 months or less. Chinese herbal medicines are also available. Bariatric surgery is also approved for severely obese subjects, but only laparoscopic sleeve gastrectomy is covered by national health insurance and some facilities implement laparoscopic sleeve gastrectomy with duodenojejunal bypass as an advanced medical treatment (JSTO 2013). Weight loss induced by GLP-1R agonists appears to be mediated through a combination of hormonal inputs to satiety centers (van Bloemendaal et al. 2014) and has not been consistently associated with changes in mental health or with potential for addiction in long-term studies conducted to establish cardiovascular safety in patients with diabetes (Marso et al. 2016a; Marso et al. 2016b; Gerstein et al. 2019). Tirzepatide, which is both a GLP-1R and GIPR agonist, has been associated with significant dose-dependent weight loss at 5-, 10-, and 15-mg doses in Phase 2 studies (Frias et al. 2018).

Dose selection for obesity treatment has been informed by 4 clinical trials: 2 Phase 1 studies (Study I8F-MC-GPGA [GPGA] and I8F-JE-GPGC [GPGC]), and 2 Phase 2 studies (Study I8F-MC-GPGB [GPGB] and I8F-MC-GPGF [GPGF]).

Phase 1 Study GPGA was a combination of single ascending dose and multiple ascending dose studies in healthy subjects and a multiple dose study in patients with T2DM. A total of

142 participants (89 healthy subjects and 53 patients with T2DM) received at least 1 dose of treatment. Doses of tirzepatide ranged from:

- 0.25 mg to 8 mg in the single ascending dose study (with maximum tolerated dose achieved at 5 mg)
- multiple doses from 0.5 mg to 4.5 mg QW and titrated doses up to 10 mg QW for 4 weeks in healthy subjects

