- multiple doses at 0.5 mg and 5 mg QW and titrated up to 15 mg QW for 4 weeks in patients with T2DM in the multiple ascending dose study

The safety and tolerability and pharmacokinetic/pharmacodynamic (PK/PD) profiles of tirzepatide at doses and escalation regimens administered in this Phase 1 study supported further development of tirzepatide for QW dosing in patients with T2DM.

In addition, the safety, tolerability, and PK/PD of tirzepatide were evaluated in Study GPGC; a Phase 1, 8-week multiple ascending dose study in Japanese patients with T2DM. This study involved a comparison of 3 QW, SC dose levels of tirzepatide or placebo:

- 2.5-mg to 10-mg titration regimen for Cohort 1
- 5-mg to 15-mg titration regimen for Cohort 2
- 5-mg fixed dose for Cohort 3

The safety and tolerability data and PK/PD profiles of tirzepatide in Study GPGC supported the use of doses up to 15 mg of tirzepatide in Japanese patients.

Phase 2 Study GPGB provided initial safety, tolerability, and efficacy data in the tirzepatide 1- to 15-mg dose range when used in treatment of patients with T2DM. In the dose range of 5 to 15 mg, tirzepatide provided significantly greater reductions in hemoglobin A1c (HbA1c) and body weight compared with dulaglutide 1.5 mg QW. The most common adverse events (AEs), which were also dose dependent, were mild-to-moderate nausea, vomiting, and diarrhea (Frias et al. 2018).

Phase 2 Study GPGF showed that adjustments in the tirzepatide dose-escalation algorithms resulted in additional reduction in the frequency of gastrointestinal (GI) AEs and reduced the frequency of treatment discontinuations due to GI AEs. Dose-escalation algorithms starting at a low dose of 2.5 mg accompanied by dose escalation of 2.5-mg increments every 4 weeks should permit time for development of tolerance to GI events and are predicted to minimize GI tolerability concerns. The maximum proposed dose of 15 mg maintains an exposure multiple of 1.6 to 2.4 to the no-observed adverse-effect level doses in 6-month monkey and rat toxicology studies. Based on interim data in Study GPGC, there were no clinically meaningful differences in the PK, PD, and safety profile between Japanese patients and non-Japanese patients with T2DM. Hence, the doses and associated escalation schemes chosen for this Phase 3 Study GPHZ are the same as that chosen for global studies.

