4.3. Justification for Dose

Tirzepatide doses of 10 and 15 mg QW will be evaluated in this study.

These doses and associated escalation schemes were selected based on assessments of safety, efficacy (glycemic and weight loss effect), and GI tolerability data, followed by data from exposure response modeling in participants with T2DM in Phase 1 and 2 studies.

Dosing scheme starting at a low dose of 2.5 mg accompanied by a gradual dose escalation of 2.5-mg increments every 4 weeks should allow the development of tolerance to GI events and intends to minimize GI AEs.

The maximum proposed dose of 15 mg maintains an exposure multiple of 1.6 to 2.4 to the no observed adverse-effect level doses in 6-month monkey and rat toxicology studies.

The selected dose and escalation scheme would enable further evaluation of benefit/risk considerations for 10-mg and 15-mg doses of tirzepatide.

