- a. Male participants:
 - Male participants with partners of childbearing potential should be willing to use reliable contraceptive methods throughout the study and for 5 half-lives of study intervention plus 90 days, corresponding to 4 months after the last injection.
- b. Female participants:
 - i. Female participants of childbearing potential (not surgically sterilized and between menarche and 1-year postmenopausal) must:
 - A. test negative for pregnancy at Visit 1 based on a serum pregnancy test.
 - B. if sexually active, agree to use 2 forms of effective contraception, where at least 1 form is highly effective, for the duration of the trial and for 30 days thereafter, and
 - C. not be breastfeeding
 - ii. Women not of childbearing potential may participate and include those who are:
 - A. infertile due to surgical sterilization (hysterectomy, bilateral oophorectomy, or tubal ligation), congenital anomaly such as Mullerian agenesis; or
 - B. post-menopausal defined as either
 - A woman at least 40 years of age with an intact uterus, not on hormone therapy, who has cessation of menses for at least 1 year without an alternative medical cause, AND a follicle-stimulating hormone >40 mIU/mL; women in this category must test negative in pregnancy test prior to the study entry

or

• A woman 55 or older not on hormone therapy, who has had at least 12 months of spontaneous amenorrhea

or

 A woman at least 55 years of age with a diagnosis of menopause prior to starting hormone replacement therapy

Informed Consent

5. Capable of giving signed informed consent as described in Appendix 1 (Section 10.1), which includes compliance with the requirements and restrictions listed in the informed consent form (ICF) and in this protocol

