8.9. Immunogenicity Assessments

At the visits and times specified in the Schedule of Activities (Section 1.3), venous blood samples will be collected to determine antibody production against tirzepatide.

To interpret immunogenicity results, a venous blood sample will be collected at the same time points to determine the blood concentration of tirzepatide. All samples for immunogenicity should be taken predose when applicable and possible. The actual date and time (24-hour clock time) of each sampling will be recorded. Immunogenicity will be assessed by a validated assay designed to detect ADAs in the presence of tirzepatide at a laboratory approved by the sponsor. Antibodies may be further characterized for cross-reactive binding to endogenous counterparts, and their ability to neutralize the activity of tirzepatide or endogenous counterparts. Sample collected at Visit 801 will assess immunogenicity at washout of tirzepatide (5 half-lives post end of treatment).

Treatment-emergent ADAs are defined in Section 9.4.5.

Long-term sample retention is defined in Section 10.1.11.

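### The restart rule for three or more missed doses sends participants who have never received 5 mg straight to 5 mg (low severity, cheap to improve)

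*Protocol*

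**What the plan says.** The planned start is in the Synopsis (Protocol Section 1.1): "The starting dose of tirzepatide will be 2.5 mg QW (or matching placebo) for 4 weeks", followed by 2.5 mg steps every four weeks up to 10 or 15 mg. The reason is GI tolerability. Section 2.2 says that "2.5-mg increments every 4 weeks should permit time for development of tolerance to GI events", and Section 4.3 repeats the argument: "Dosing scheme starting at a low dose of 2.5 mg accompanied by a gradual dose escalation of 2.5-mg increments every 4 weeks".

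Section 7.1.1 sets the restart dose by the length of the gap alone. After one or two missed doses, the "participant restarts study drug at last administered dose, as per escalation schedule". After three or more, the "participant restarts study drug (at 5 mg, managed by IWRS) and repeats dose escalation scheme". Intolerable persistent GI events have a separate row that points to Section 10.8. Section 6.7.1 refers interruptions of more than one dose back to Section 7. No readable text in the protocol or SAP makes an exception for participants who are still on 2.5 mg.

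**The concern.** The rule for long gaps works as a step back for almost everyone. A participant on 7.5 mg or above drops to 5 mg, and one on 5 mg resumes a dose already taken. Only for a participant who has not got past 2.5 mg does the same row act as a step up. That participant receives a dose never taken before, double the last one, at the moment when least drug remains from earlier injections.

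What is at stake is tolerability in a small, identifiable group. If intolerable GI symptoms persist at 5 mg, the example in Section 6.7.1 reduces anyone on 10 mg or lower to placebo and allows only one reduction. On that text, a participant who cannot tolerate the 5 mg restart has no lower active dose to fall back on.

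**Working it through.** **The plan's own figure.** From 2.5 to 15 mg there are (15 − 2.5)/2.5 = 5 steps; 5 × 4 weeks = 20 weeks, which matches the stated 20-week escalation. To 10 mg it is 3 × 4 = 12 weeks. From a 5 mg restart it is 16 weeks to 15 mg and 8 weeks to 10 mg.

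**Who is affected.** Let k be the number of 2.5 mg doses taken (Weeks 0 to k − 1) and g the number of consecutive doses missed. The restart is at Week k + g. A participant has not yet had 5 mg if k is 1, 2, 3 or 4, that is, if the gap starts at Week 1, 2, 3 or 4. With g = 3, the restart is at Week 4, 5, 6 or 7, always 28 days after the last injection. Longer gaps give a longer interval.

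**Drug remaining.** The documents state no half-life, but two places imply one.
- Section 8.9: "Sample collected at Visit 801 will assess immunogenicity at washout of tirzepatide (5 half-lives post end of treatment". Visit 801 is 4 weeks after the end of treatment, so 28/5 = 5.6 days. If the last dose was at Week 71, the interval is 35 days and the half-life 7 days.
- Section 5.1: "5 half-lives of study intervention plus 90 days, corresponding to 4 months after the last injection". Four months is 120–122 days; less 90 days this leaves 30–32 days, or 6.0–6.4 days per half-life.

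Assuming first-order elimination, the fraction of the last dose left at day 28 runs from 0.5^(28/5.6) = 3.1% to 0.5^(28/7) = 6.25%.

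In mg-equivalents, summing 2.5 × 0.5^(days since dose / half-life) over the doses taken gives, at restart:
- half-life 5.6 days: 0.08, 0.11, 0.12 and 0.13 for k = 1 to 4;
- half-life 7 days: 0.16, 0.23, 0.27 and 0.29.

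In an uninterrupted participant at Week 4, the same sum over doses 28, 21, 14 and 7 days earlier is about 1.76 (5.6 days) or 2.34 (7 days). The planned first 5 mg dose is therefore added to substantial carry-over. The restart dose is added to almost none, and this is so whether one or all four 2.5 mg doses had been taken.

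**Time at target up to Week 72, three-dose gap.**

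| Gap starts at Week | Restart Week | 15 mg from: now / 2.5 mg restart | Weeks at 15 mg: now / 2.5 mg restart | Weeks at 10 mg: now / 2.5 mg restart |
|---|---|---|---|---|
| 1 | 4 | 20 / 24 | 52 / 48 | 60 / 56 |
| 2 | 5 | 21 / 25 | 51 / 47 | 59 / 55 |
| 3 | 6 | 22 / 26 | 50 / 46 | 58 / 54 |
| 4 | 7 | 23 / 27 | 49 / 45 | 57 / 53 |

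The 10 mg column is for participants randomized to 10 mg (10 mg from Week k + 11 now, k + 15 with a 2.5 mg restart). No input to the sample-size calculation enters any of this. The SAP's primary estimand (Section 1.1.2.1) already counts temporary interruptions and modifications before discontinuation as part of the treatment condition.

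**The case against.** The strongest reply is that nothing in the documents shows harm from starting at 5 mg. That stands. A reader might take the Phase 1 result in Section 2.2, a "single ascending dose study (with maximum tolerated dose achieved at 5 mg", as a warning, but a maximum tolerated dose is one that was tolerated, and the study went up to 8 mg. Section 2.2 also reports Japanese cohorts with type 2 diabetes that began at 5 mg without a 2.5 mg lead-in, and says the study supported doses up to 15 mg in Japanese patients. This trial excludes diabetes, so the match is imperfect, but the evidence leans towards reassurance.

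Three further replies also stand in part:
- No passage fixes four 2.5 mg doses as a minimum, and Section 6.4 counts three of four doses in a visit interval as compliant. A line drawn at fewer than four doses would be arbitrary: someone with four doses and the same gap is also facing a first 5 mg dose after near-washout. The defensible line is whether 5 mg has ever been received.
- A reader might infer that the rule jumps ahead of schedule, or that a short gap is treated more cautiously than a long one. Neither is established. The restart is at Week 4 or later, when 5 mg is already the calendar dose. The contrast with the short-gap row exists only if the last administered dose is read by dose rather than by calendar.
- The IWRS may hold an unstated rule, and the Section 10.8 chart is not readable here. However, Section 7.1.1 sends only intolerable persistent GI events to that chart. Interruptions for other reasons stay under this row, and a rule that exists only in the IWRS should be written into it.

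How much GI tolerance survives a 28-day gap is not documented either way.

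**Conclusion.** The point holds as a low-severity improvement. Followed as written, Section 7.1.1 gives a participant who has not got beyond 2.5 mg a first 5 mg dose (or matching placebo) 28 or more days after the last injection, about five half-lives by the protocol's own account, without the stepwise build-up that the protocol plans. The residual of roughly 3% to 6% rests on first-order elimination and an inferred half-life of 5.6 to 7 days. The group is limited to gaps of three or more doses starting at Weeks 1 to 4. Its size cannot be derived from the documents and is probably small. A conclusion that the 5 mg restart is unsafe would go beyond the documents. Alpha, power and the estimand are unaffected.

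**What to change.** Add to the row for three or more missed doses, and to the matching IWRS logic: a participant who has not yet received any 5 mg dose (or its matching placebo step) restarts at 2.5 mg or matching placebo for four weekly doses, then escalates as scheduled. All others restart at 5 mg as now.

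This needs one table clause, one IWRS rule and no added participants. The target dose is reached 4 weeks later. For a three-dose gap, time at 15 mg becomes 45–48 weeks, against the 52 planned in Section 4.2. The current rule already falls short for gaps starting at Weeks 2 to 4 (49–51 weeks). Time at 10 mg stays above 52 weeks.

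Supply needs attention. Under both rules, gaps starting at Weeks 2 to 4 put dose steps between dispensing visits, so some visits must supply two strengths. Under the fix this includes Week 24, because 15 mg falls due at Weeks 25 to 27 and the next dispensing visit is Week 36. A longer gap may need the Week 28 telephone visit held in the office, which the Schedule of Activities allows. For example, four doses missed from Week 4 means a restart at Week 8 and 15 mg at Week 8 + 20 = 28.
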